## 15 SAFETY ANALYSES

No statistical tests for comparison of safety data between treatment groups will be performed.

Safety data will be summarized descriptively by treatment group and by visit if applicable.

All safety data will be presented for the SAF unless otherwise specified.

The interim integrated clinical trial report will report all safety data until the cut-off date (last subject performing its Visit 11 (Week 26)), regardless of whether data is assessed before or after Visit 11.

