For all enrolled subjects, the incidence, incidence rate, the number of events and the percentage of events (related to the total number of events) will be summarized by SOC and PT (sorted alphabetically) for each:

- Pre-treatment non-TEAEs.
- Serious pre-treatment non-TEAEs.

Presentation will only be overall and not per treatment.

The number and percentage of events will be summarized by SOC and PT (sorted alphabetically) for the following TEAE descriptors:

- Intensity: mild, moderate, severe.
- Causal relationship to the IMP: related (with sub-categories: possible, probable/likely, certain), not related (with sub-categories: not related, unlikely), unknown (with sub-categories: conditional/unclassified, unassessable/unclassifiable, causal relationship missing).
- Outcome: recovered/resolved, recovering/resolving, not recovered/not resolved, recovered/resolved with sequelae, fatal, unknown.
- Non-IMP related countermeasures: none, newly started medication, trial discontinuation, others.
- Action taken with IMP: drug interrupted, drug withdrawn, dose not changed, not applicable, unknown.

Denominator for percentage calculation will be the number of all TEAEs for presentation of overall SOCs, and the number of TEAEs per SOC or PT respectively, for the presentation per SOC or PT, respectively.

Measures of location and variation will be calculated for:

- Duration of TEAEs.
- Time to onset of TEAE (days).

In addition, the time to onset of TEAEs will be summarized using time-to-event methods for the overall 5 most frequent TEAEs. Time will be weeks, until onset.

The following listings will be produced for all enrolled subjects:

- Deaths.
- Serious adverse events other than death.
- Adverse events leading to discontinuation from the trial.
- Adverse events leading to discontinuation from IMP.
- Adverse events leading to IMP dose decrease or interruption of IMP.
- Adverse events associated with the acute phase reaction.

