#### **Handling of missing date information**

The term missing date/time refers to a completely missing date /time or to an incomplete date/time where parts are not available e.g., missing hours.

The following imputation strategy is applied.

If the number of adverse events with missing date/time information exceeds 10%, the imputation strategy is only applied to assess if an adverse event is a TEAE but not for any other calculation (e.g., duration, onset).

Missing start and end date/times will be imputed conservatively, i.e., missing values will be imputed in such a way that the duration of the adverse event is considered with the longest possible duration and such that, whenever the adverse event may potentially start after first IMP administration, the adverse event will be handled as a TEAE.

I1-I4: imputation steps

C1-C4: checkpoints

AE = adverse event, IMP = investigational medicinal product

Figure 1: Graphical overview about the imputation strategy

Further explanations on the flow chart:

The different steps of the displayed imputation strategy must be completed from the first to the last step. All procedures in each step must be completed in the order given.

- Imputation:
  - I1: Impute with date/time of first IMP  
{If administration of IMP was not collected with time information set adverse event start time to 00:00.}
  - I2:
    - a) Impute with first calendar day and/or first calendar month  
Imputation will be done based on the available partial information starting with month and then day. The respective first month and day will be chosen for imputation:

Missing date	Imputed date
2014-Mar	2014-Mar-01
2014	2014-Jan-01

- b) Impute with first hour and/or first minute  
Imputation will be done based on the available partial information starting with hour and then minutes. The respective first hour of a day and first minute will be chosen for imputation. “00:00” will be considered as the first hour/first minute per day.

Missing time	Imputed time
11:--	11:00
--:--	00:00

}

- I3: Impute with date/time of informed consent signed  
If signing of informed consent was not collected with time information, set the adverse event start time to 00:00.
- I4:
  - a) Impute with last calendar day and/or calendar last month  
Imputation will be done based on the available partial information starting with month and then day. The respective last month and day will be chosen for imputation:

Missing date	Imputed data
2014-Mar	2014-Mar-31

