2014	2014-Dec-31

For February leap years must to be taken into account when calculating the last day in February.

- 1.1. b) Impute with last hour and/or last minute  
Imputation will be done based on the available partial information starting with hour and then minutes. The respective last hour of a day and last minute will be chosen for imputation. “23:59” will be considered as the last hour/last minute per day.

Missing time	Imputed time
11:--	11:59
--:--	23:59

- Checkpoints
  - C1: The decision must be taken based on the available information (date /time) before imputation.
  - C2: Adverse event stop date before first IMP
- 1.2. 1) The decision must be taken based on the available information (date/time) before imputation.
  - 2) If the end date is completely missing (with or without the information that the adverse event was continuing), this will be considered as after first IMP.
  - 3) If no IMP was given, this will be treated as adverse event stop date before the first IMP.
  - C3: The decision must be taken based on the available information (date/time) before imputation.
  - C4: The decision must be taken based on the available information (date/time) before imputation.

A replacement of missing year for adverse event start information is not foreseen. If needed, this will be considered on a case-by-case decision which must be documented together with the documentation of ADaM data sets.

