**Duration of adverse events**

Duration of adverse event will be calculated based on the imputed values for adverse event start date/time and stop date/time.

If the duration of the adverse event could not be calculated due to unknown date information, the following assessment to categories will be used:

- If the adverse event is marked as “continuing” in the {e-}CRF, the duration will be categorized as “continuing”.
- Otherwise, the duration category will be set to “missing”.

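### Summaries of adverse event duration leave out events still continuing, so persistence is understated and differences in persistence between arms are shrunk

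*SAP*

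**What the plan says.** - **Summary planned.** SAP 15.1.2: "Measures of location and variation will be calculated for" duration of TEAEs and time to onset. Time-to-event methods are then added for onset of the five most frequent TEAEs, but not for duration.
- **Derivation.** SAP 19.1.6.1, Duration of adverse events: "Duration of adverse event will be calculated based on the imputed values for adverse event start date/time and stop date/time".
- **When no number is possible.** Same section: "If the duration of the adverse event could not be calculated due to unknown date information", an event ticked as continuing in the eCRF is handled so that "the duration will be categorized as" continuing. Any other such event is set to missing.
- **Stop-date imputation.** SAP 19.1.6.1, step I4: "Imputation will be done based on the available partial information starting with month and then day". It completes partial dates to the latest possible value.
- **Cut-off.** SAP 15: "The interim integrated clinical trial report will report all safety data until the cut-off date", which is the last subject's Visit 11, whether the data arose before or after a subject's own Visit 11.
- **Protocol.** Section 14.1.8.1 promises a summary of duration without naming a method. Section 12.4.1 collects adverse events up to the last scheduled contact, and the eCRF takes either an end date or continuation.

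**The concern.** An event still open at last contact or cut-off is known to have lasted at least as long as it was observed. That is a right-censored duration. Giving it a category and computing location and spread from the rest removes information mainly from the upper tail. How long reactions persist is an ordinary tolerability question, and here the answer would be too short by an amount that depends on the proportion still open. If one arm has more persistent events, more of its long durations are removed, so the difference the table is meant to show is reduced. SAP 8.1 already describes Kaplan-Meier summaries with numbers at risk and censored. SAP 15.1.2 applies such methods to onset and leaves out duration, where open events arise as a matter of course.

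**Working it through.** **1. Does any rule give a continuing event a number?** The candidates, in turn:
- The duration rule needs a stop date.
- Step I4 needs a partial stop date to work on; a continuing event has none.
- Checkpoint C2 addresses a completely missing end date, but only to decide whether the event ended before first dosing. It assigns no date.
- No rule sets the stop date to last contact or cut-off.

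The flow chart (Figure 1) was not available for this check, so the reading rests on the written steps. It is supported by the existence of the *continuing* category, which would have little purpose if stop dates were filled in for such events.

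**2. Size.** The documents give no duration figure, so there is none to reproduce. Everything below is illustration under stated assumptions.

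*Closed form.* Let durations be exponential with true median m and follow-up after onset be c. Write x = 2^(−c/m). Then
- share ongoing = x
- ended-only median = −m · log2[(1 + x)/2]

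Take m = 90 days and onset in Days 0 to 15 (average 7.5):
- Follow-up 365 days: c = 357.5, x = 0.064, ended-only median = −90 · log2(0.532) ≈ 82 days.
- Follow-up 183 days: c = 175.5, x = 0.259, ended-only median = −90 · log2(0.629) ≈ 60 days.
- With m = 3 days, x is effectively 0 and there is no bias.

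*Simulation* (exponential, 400,000 events per setting), ended-only median in days:

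| Follow-up, onset | true 3 | true 30 | true 90 | true 180 |
|---|---|---|---|---|
| 365 d, Days 0–15 | 3.0 | 30.0 | 81.9 | 121.7 |
| 365 d, uniform | 3.0 | 26.3 | 57.8 | 77.2 |
| 183 d, Days 0–15 | 3.0 | 29.3 | 59.8 | 73.3 |
| 183 d, uniform | 2.9 | 22.6 | 38.7 | 45.4 |

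The Kaplan-Meier median, with ongoing events censored, returns about 3, 30, 90 and 180 days in every row. The 183-day rows are a floor: they give every subject the shortest follow-up of a completer.

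*Follow-up as the SAP defines it.* In the 26-week report, subjects allocated early have more than 26 weeks of data. Assume follow-up uniform on 183 to 365 days and log-normal durations with median 7 days and log SD 2.0, so the true upper quartile is 7 · exp(0.6745 · 2.0) ≈ 27 days. Half of onsets fall in the first 10 days. By simulation:
- Other onsets spread over 26 weeks: 5.0% ongoing, ended-only median 6.2 days, upper quartile about 22 days.
- Other onsets spread through follow-up: 7.7% ongoing, ended-only median 5.8 days, upper quartile about 20 days.

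**3. Effect on a comparison.** Take arms with true medians of 30 and 90 days, a difference of 60. From the table, the ended-only differences are 81.9 − 30.0 = 51.9, 57.8 − 26.3 = 31.5, 59.8 − 29.3 = 30.5 and 38.7 − 22.6 = 16.1 days. The difference shrinks in every setting and keeps its sign.

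**The case against.** **Information on open events is already planned.** *Continuing* is kept apart from *missing*, SAP 15.1.2 tabulates outcome including events not recovered, and SAP Table 3 prints the number missing beside the mean and median. This stands in large part. It shows how many events persist, but not for how long, and it does not correct the mean or median.

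**The stakes are low.** Safety is descriptive with no tests between arms (SAP 15), and the protocol fixes no method. This stands, and it limits the weight of the point.

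**Kaplan-Meier on events has its own faults.** One subject can contribute several events, so standard intervals are unreliable, and the SAP 8.1 default censors at Visit 11 in the Week 26 report. Both stand and are dealt with in the fix.

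**Readings that go too far.** A reader might infer any of the following:
- *That the arm with more persistent events would look shorter.* The two-arm figures do not show this: the ended-only statistic still rises with true persistence.
- *That acute phase reactions would be reported as too short.* Events of a few days near the infusions show essentially no bias, and most terms in the SAP's acute-phase group count only if they last no more than 3 days.
- *That the longest events are always the ones left out.* This is a tendency. An event beginning just before last contact is also continuing. With uniform onset, 3 to 16% of ongoing events would in truth last less than the ended-only median.
- *That all follow-up in the 26-week report stops at about Day 182.* Under the same log-normal assumptions that would put 10% of events ongoing, but the SAP 15 cut-off is the last subject's Visit 11 and includes later data from earlier subjects.

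Partial dates are also imputed to the longest possible duration, a probably small bias in the other direction.

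**Conclusion.** The point holds with modest weight. As written, the duration statistics describe events with a known or imputable stop date, and they understate duration whenever events remain open. The direction follows from the text; the size does not, because it depends on durations, onset times and follow-up that the documents do not give. Under the log-normal assumptions with follow-up of 183 to 365 days, the median falls by about 1 day in 7 and the upper quartile by about 5 to 7 days in 27. For events lasting months the loss is larger: a true median of 90 days appears as 39 to 82 days across the exponential settings. The affected results are persistent and late-onset events, more so in the 26-week report.

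**What to change.** In SAP 15.1.2, add that TEAE duration is summarised by Kaplan-Meier (median, quartiles, number censored), at least for the most frequent terms. In SAP 19.1.6.1, state that an event marked continuing is censored at the subject's last contact or the report's data cut-off, whichever comes first, as an explicit exception to the SAP 8.1 default of censoring at Visit 11. Either use one event per subject and term, or use intervals clustered by subject, or omit the confidence intervals.

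If the mean and SD are kept, label them as covering events with a known stop date and print the number and percentage continuing by arm beside them.

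The cost is SAP wording and one changed table, with no new data collection. Upper quartiles may not be estimable for rare terms.

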## 15.2 Laboratory parameters, vital signs and ECG parameters

This section defines the general principles for the analysis of categorical and continuous parameters, unless specified otherwise. In general, the analysis of all parameters will be done by visit and by treatment group.

Categorical parameters will be descriptively summarized per visit and overall post-baseline. For an overall post-baseline analysis, the worst value during the on-treatment period, including unscheduled visits, will be derived.

If applicable, the number of not exact values will be displayed in the respective table. Continuous parameters will be descriptively summarized. Changes from baseline will be presented for all post-baseline visits. Baseline values are defined as described in Section 8.2.2.

Where applicable, continuous parameters laboratory, vital signs, ECG parameter will be classified as *low*, *normal*, or *high* based on reference ranges and for parameters where sponsor alert ranges are defined as *alert low*, *non-alert*, or *alert high* (for laboratory parameters alert ranges are transferred with the data, for vital signs and ECG see Section 19.3). For an overall post-baseline analysis, values during the on-treatment period, including unscheduled visits, will be considered. If a subject has parameter values flagged as *low* and values flagged as *high*, the parameter will be classified as *low+high*, *alert low + alert high*, respectively.

A summary of the number and the percentage of subjects with values flagged as *alert low*, *non-alert*, *alert high* with respect to alert ranges will be provided for each continuous parameter.

Shift tables from baseline for the different visits and overall post-baseline will be generated for each continuous parameter flagged as *low*, *normal*, or *high* with respect to reference ranges. Denominator for the percentage calculation within each baseline category (*low*, *normal*, or *high*) will be the number of subjects at the respective visits.

Graphical presentations of the time course of specific continuous parameters and corresponding changes from baseline will be provided (mean and 95% confidence interval). At each visit, the plots will show the total number of subjects by treatment. On the bottom, the number of subjects flagged as *low*, and on the top the number of subjects flagged as *high* based on reference ranges (and *alert low* or *alert high* based on alert ranges), will be shown by treatment.

Shift plots by visit will be provided for specific continuous parameters with reference ranges and sponsor-defined alert ranges marked by vertical and horizontal lines}.

A listing of subjects with values outside the sponsor-defined alert ranges will be provided.

All parameter values will be presented in a subject data listing including respective flagging with respect to reference ranges and to sponsor-defined alert ranges.

Unscheduled measurements of parameters will be presented in the subject data listing. In general, unscheduled measurements will not be included in the analysis. However, they will be taken into account in the calculation of the overall post-baseline classification of parameters.

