14.1.8.2 Safety laboratory values, vital signs, 12-lead ECG

Safety laboratory values, vital signs, and 12-lead ECG (including changes from baseline as applicable) will be descriptively summarized per visit.

Baseline will be the value collected on Day 1 (Visit 2) prior to first administration of IMP.

A listing of subjects with values outside the sponsor-defined alert ranges will be provided.

The ECG printouts will be interpreted by the investigator as “normal”, “abnormal, but clinically not relevant”, or “abnormal and clinically relevant”. Results from this interpretation will be reported in subject data listings.

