**8.2.2 Further definitions**

Baseline	
Baseline is defined as the last observation (scheduled or unscheduled) before first IMP administration if not otherwise specified. In general, baseline is the value recorded at Visit 2.
 
More precisely, for post-baseline comparisons of all parameters except pain intensity in the eDiary, the assessment before first IMP administration at Visit 2 (Day 1) will serve as the baseline based on recorded date/times. In case the value planned on Day 1 is missing or in case there are multiple values before first IMP administration on Day 1, the last scheduled or unscheduled non-missing value before first IMP administration will be used.
 
For current, average, and worst pain, baseline pain intensity will be calculated as the average of the non-missing pain intensity ratings obtained over the 7-day baseline pain assessment phase prior to first IMP administration.

Investigational Medicinal Products (IMP)	The IMPs used in this trial are neridronic acid and matching placebo.
On-treatment-period	For the purpose of this trial, the on-treatment period starts at the first IMP administration (included) and continues until the date (included) when the subject leaves the trial, i.e., at the Final Visit (Visit 17, week 52 after Follow up period 2) for trial completers, and otherwise at the End of Trial date for subjects not fully completing the trial. The on-treatment period extends beyond the dosing period. This is because of the persistence in bone and potentially prolonged effect of neridronic acid.
Pooling of sites	Individual sites will be pooled by geographic region. Geographic regions are defined as USA/Canada, Europe, and Other Regions (including Asia-Pacific and Australia/New Zealand).
Pre-treatment-period	Before the first IMP administration (excluded).
Treatment Period A completers	
Treatment Period A completers are treated subjects who completed IMP administration in Treatment Period A according to the protocol, i.e., subjects who received the full dose of all 4 planned infusions.
 
Subjects are identified via the “Treatment Period A completer” page in the CRF based on the data point “Did the subject complete the treatment?”

Follow-up Period 1 completers	Follow-up Period 1 completers are treated subjects who completed the Follow-up Period according to the protocol, i.e., subjects who have a Visit 11 not before Day 183. Subjects do not need to be Treatment A completers.

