### **14.2 Bone turnover markers and markers for disease severity or CRPS progression**

Bone turnover markers will be analyzed in the PDS. Soluble interleukin-2 receptor (sIL-2R) will be analyzed in the SAF.

The following bone turnover markers are assessed:

- Bone formation markers:
  - Procollagen type I amino-terminal propeptide (PINP).
  - Bone alkaline phosphatase (BAP).
- Bone resorption marker:
  - C-terminal telopeptide of type I collagen (CTX).

All bone turnover marker data will be listed in a subject data listing.

Bone turnover marker values as well as sIL-2R values, including changes from baseline, will be descriptively summarized by parameter and time point. Baseline is defined by the value on Day 1 (Visit 2).

For bone turnover markers as well as sIL-2R values a graphical plot of the mean and 95% CI of bone turnover marker values over time will be presented. Similarly, a plot of the mean change from baseline of bone turnover marker values over time will be presented. Furthermore, a display by fasting and non-fasting status will be done as assessed on the 'Date of confirmed Visit' in the eCRF. The non-fasting status consists out of non-fasting, insufficient fasting and unknown categories.

All bone turnover marker data and sIL-2R data will be listed in a subject data listing.

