**Time to onset of adverse events**

Time to onset of adverse events will be calculated based on the first administration of IMP based on the imputed value for adverse event start date/time.

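### Period B safety changes are referenced only to Visit 2 and event onset only to the first IMP dose, so no within-subject change from the pre-infusion Visit 11 value and no Period B onset time is planned

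*SAP*

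**What the plan says.** SAP 8.2.2 gives one general rule: "Baseline is defined as the last observation (scheduled or unscheduled) before first IMP administration if not otherwise specified". For everything except diary pain it adds that "the assessment before first IMP administration at Visit 2 (Day 1) will serve as the baseline". SAP 15.2 adopts this for laboratory values, vital signs and ECG ("Baseline values are defined as described in Section 8.2.2") and applies it to every later visit: "Changes from baseline will be presented for all post-baseline visits". Shift tables use the same baseline. Protocol 14.1.8.2 agrees: "Baseline will be the value collected on Day 1 (Visit 2) prior to first administration of IMP". SAP 14.2 also sets the bone marker and sIL-2R baseline at Visit 2.

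For adverse events, SAP 19.1.6.1 states: "Time to onset of adverse events will be calculated based on the first administration of IMP". SAP 15.1.2 then summarises time to onset in days and, for the five most frequent events, by time-to-event methods in weeks. SAP 8.2.2 defines IMP as neridronic acid or matching placebo.

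Neither document defines a second safety reference for Period B. For efficacy the SAP does have one: change or shift from Week 26 is planned for tablet pain (13.3.1), PGI-S (13.3.7) and EQ-5D-5L (13.3.8).

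**The concern.** Protocol 8.1 includes the second course partly to obtain safety and tolerability data, and so that subjects first given placebo can receive active drug. For those subjects the Visit 11 infusion is their first neridronic acid. For the others it is a re-exposure. In both groups the natural safety question is what happened after that infusion relative to just before it.

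A change from Visit 2 answers a different question. It adds about half a year of drift to the response, and for subjects first given neridronic acid it also adds the first course. The protocol itself allows changes in that interval that could move these parameters: extra calcium or vitamin D supplementation between Visits 10 and 11 (1.3.3), and the end of the restriction on NSAIDs and similar agents two weeks after the last infusion of a period (1.4.2.1).

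The onset clock has the same fault in a plainer form. For a subject first given placebo, the time from first neridronic acid exposure to an event is never calculated.

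**Working it through.** **Inputs.** Planned days are Visit 2 = Day 1, Visit 11 = Day 183 (window +7 days), and Visits 12 to 17 = Days 186, 189, 192, 197, 253 and 365 (SAP 19.1.1.9, Protocol 1.7.2). By SAP 19.1.1.4, trial day = date − Day 1 + 1, so elapsed days = trial day − 1.

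**1. The plan's own timing.** 183 − 1 = 182 days, and 182/7 = 26.0 weeks, which reproduces Week 26. At the end of the window, 190 − 1 = 189 days = 27.0 weeks.

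**2. Age of the reference at each Period B visit (days, Visit 11 on Day 183).**

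| Visit | From Visit 2 (planned) | From Visit 11 |
|---|---|---|
| 12 | 185 | 3 |
| 13 | 188 | 6 |
| 14 | 191 | 9 |
| 15 | 196 | 14 |
| 16 | 252 | 70 |
| 17 | 364 | 182 |

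**3. Onset of an event on Day 184.** From first IMP: 184 − 1 = 183 days (26.1 weeks). From the first Period B infusion: 184 − 183 = 1 day. This needs no assumption.

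**4. Is a better reference collected?** Yes. At Visit 11, laboratory sampling must precede the infusion, and vital signs and triplicate ECGs are taken before and after it (Protocol 1.7.2, footnotes e, f and m; 11.1.4.1.1). Bone markers are not drawn at Visit 11. The last sample before it is Visit 10, Day 155, which is 183 − 155 = 28 days earlier (Protocol 11.1).

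**5. Which displays are affected.**
- Change from baseline: laboratory values, vital signs and ECG intervals including QTcF. No change from Visit 11 is planned for any of them.
- Laboratory shift tables: Period B entry (Protocol 1.3.3) requires the last calcium and magnesium before Visit 11, and potassium at Visit 10 or on its one repeat, to be in range. Calcium and magnesium had to be in range before Visit 2 as well. For these the two references will usually fall in the same category. Entry only caps others: eGFR not below 30 mL/min/1.73 m², ACR not above 150 mg/g, ALT and AST not above 2 × ULN. Creatinine has no limit of its own. A subject may therefore be outside the reference range for these at Visit 11 and still be counted as a shift from Visit 2 at Visits 12 to 17.
- QTcF: SAP 15.2 builds shift tables on reference ranges, and SAP 19.3 defines none for ECG parameters. There is no such QTcF table to distort.

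**6. Spread of the change.** With equal variances, SD of change = σ√(2(1 − ρ)). The ratio of the SD from Visit 2 to the SD from Visit 11 is √((1 − ρ_long)/(1 − ρ_short)). The documents give no correlations, so these are assumptions:

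| ρ_long | ρ_short | Ratio |
|---|---|---|
| 0.6 | 0.9 | √(0.4/0.1) = 2.00 |
| 0.8 | 0.9 | √(0.2/0.1) = 1.41 |
| 0.7 | 0.8 | √(0.3/0.2) = 1.22 |
| equal | equal | 1.00 |

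A correlation over days cannot apply at Visit 16 (70 days) or Visit 17 (182 days), so any gain is smaller there.

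**The case against.** The strongest reply has four parts.

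**Period B events are already separated.** SAP 15.1 defines display by trial phase, four treatment groups and an overall neridronic acid group, and 15.1.1 applies the phase split to the overview tables. This stands. A reader might infer that Period B events are lost among Period A events, and the SAP does not support that. The split leaves the onset clock as it is, although the offset of 182 to 189 days is known for each subject.

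**Visit 11 values are shown.** By-visit means, changes, plots and listings are planned, and an abnormality at Visit 11 appears in that visit's own shift table. This stands for group means, apart from missing data. It gives no within-subject SD or shift from Visit 11. SAP 8.1 also uses two groups up to Week 26 and four afterwards, and leaves open whether Visit 11 is displayed for the same groups as Visit 12.

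**Visit 2 is a reasonable reference.** For subjects first given neridronic acid it is the only drug-free value, and the drug persists in bone. Protocol 9.3.2 (Table 2, footnote a) deliberately uses the pre-Period A eGFR for the discontinuation rule in both periods. This stands as a reason to keep the Visit 2 display. It is no reason against showing a second one, and the discontinuation rule is separate from the summary tables.

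**Nothing is tested.** SAP 15 plans no between-group tests on safety data, so extra spread changes no inference. This stands.

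**Conclusion.** The point holds as a gap in descriptive safety reporting for subjects treated in Period B. Within-subject change after the open-label infusion is measured from a value 182 to 189 days older than the first infusion, and an event one day after a Day 183 infusion is given an onset of 183 days. Both figures follow from the schedule alone. The laboratory shift part is narrower: mainly creatinine, milder eGFR and ACR changes, and ALT or AST up to 2 × ULN.

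Three stronger readings should be avoided. QTcF shift tables are not distorted, because none against reference ranges is planned. Calcium shift is little affected because of the entry rules; it is not wholly unaffected, since those rules use samples taken before Visit 11. The noise cannot be said to double: the ratio runs from about 1.0 to 2.0 across the assumed correlations, with less to gain at Visits 16 and 17.

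The primary endpoint, the sample size and the event counts are unaffected. The change is still worth making, because the data exist and the SAP already uses a Week 26 reference for efficacy.

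**What to change.** - **SAP 8.2.2:** add a Period B reference, defined as the last non-missing value before the first Period B infusion (the Visit 11 pre-infusion value; Visit 10 for bone markers).
- **SAP 15.2 and 14.2:** for subjects treated in Period B, present change from this reference at Visits 12 to 17, where measured, beside the change from Visit 2. Add shift where reference or alert ranges exist.
- **SAP 19.1.6.1:** for treatment emergent events starting after the first Period B infusion, calculate time to onset from that infusion, and carry this into the onset summaries of 15.1.2.

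The Visit 2 displays stay, and the eGFR discontinuation rule is left untouched. The cost is SAP wording, a second reference flag and onset variable in the analysis data sets, and more tables. No new visits, samples or subjects are needed.
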